## 9 SAFETY ANALYSIS

All safety analyses will be conducted using the Safety set, unless otherwise specified.

### 9.1 Adverse events

Adverse events are defined in the protocol Appendix 3.

A treatment-emergent AE (TEAE) is defined as any event not present prior to the first administration of the study drug, or any event already present that worsens in either severity or frequency following exposure to the study drug.

An AE that occurs prior to the first administration of the study drug will be considered a non-treatment emergent AE.

An overview summary will be provided for the number and percentage of subjects with any TEAE, serious TEAEs, TEAEs leading to treatment discontinuation, TEAEs leading to treatment interruption, TEAEs leading to death, TEAEs of special interest. A similar summary will be provided for study drug-related TEAEs.

All TEAEs, non-TEAEs, SAEs, AEs leading to death, and AEs of special interest (AESIs) will be presented in separate listings.

#### 9.1.1 Incidence of adverse events

If appropriate, the number and percentage of subjects reporting AEs will be tabulated by system organ class (SOC) and preferred term (PT) for all TEAEs, and separately for study drug-related TEAEs. Subjects with multiple events will be counted only once within each category. SOC and PT will be sorted in descending order of frequency overall.

#### 9.1.2 Severity of adverse events

Severity of AEs is assessed by the investigator according to CTCAE (version 5.0) as 'Mild' (Grade 1), 'Moderate' (Grade 2), 'Severe' (Grade 3), 'Life-threatening' (Grade 4), or 'Death' (Grade 5). A summary of TEAEs by severity will be presented in a table. If a subject reports multiple occurrences of the same AE, only the most severe will be counted. AEs that are missing severity will be presented in tables as severity 'Unknown'.

#### 9.1.3 Adverse events of special interest

AESIs include neurological reactions, hepatic reactions, testicular findings, and nausea/vomiting.

They will be summarized in a similar manner to that described in Section 9.1.1 for the following AESIs:

- Neurological reactions:
  - AEs reported in the SOC *Nervous system disorders and Psychiatric disorders*
  - AEs identified using Standardized MedDRA Queries (SMQ) such as *Non-infectious encephalopathy/delirium* and *Parkinson-like events*
- Hepatic reactions:
  - AEs reported in the SOC *Hepatic disorders*
  - AEs identified using SMQ such as Liver related investigations, signs and symptoms.
- Testicular findings: AEs identified using SMQ as *Fertility disorders*
- Nausea/Vomiting: AEs identified using MedDRA PTs *Nausea* and *Vomiting*.

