5.1 Inclusion criteria

Subjects are eligible to be included in the study only if all of the following criteria apply:

1. Male and female Chinese subjects aged 18 to 65 years, inclusive, at Screening.
2. Body mass index of 18.0 to 30.0 kg/m² inclusive, and a total body weight > 45 kg for females and > 50 kg for males at Screening.
3. Subjects who are overtly healthy as determined by medical evaluation, including medical history, physical examination, laboratory tests, vital signs, creatinine and estimated creatinine clearance (Cockcroft-Gault formula).
4. Subjects who are willing and able to comply with all requirements of the study, including confinement periods and ambulatory visits, all study-related procedures, treatment and observation plans, laboratory tests, lifestyle considerations, and other study procedures.
5. Willing and able to give signed informed consent as described in [Appendix 1](#), including compliance with the requirements and restrictions listed in the ICF and in this protocol.

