6.3 Assignment to study drug

All subjects signing the ICF will be assigned a subject number in the Electronic Data Capture (EDC). On Day 1 prior to the first study drug administration, eligible subjects will be randomized.

In PART-1, 32 subjects (16 in Cohort 1, then 16 in Cohort 2) will be randomized in a 3:3:2 ratio to FMGX low-dose, FMGX high-dose, or Placebo. In PART-2, 20 subjects (10 in Cohort 3 and 10 in Cohort 4) will be randomized in a 4:1 ratio to FMGX or Placebo.

Assignment to a specific treatment arm will be controlled by the Medidata Randomization and Trial Supply Management (RTSM) system, integrated with RAVE EDC.

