## 4 GENERAL STATISTICAL CONSIDERATIONS

Summary outputs will be presented by cohort and treatment as described below:

- Part-1: Oral low dose (Oral 400 mg), Oral high dose (Oral 800 mg), IV low dose (IV 600 mg), IV high dose (IV 1000 mg), Placebo (pooled cohort 1 and cohort 2)
- Part-2: IV only, IV and oral, Placebo (pooled cohort 3 and cohort 4).

Data from Part-1 and Part-2 will be summarized in separate tables and figures.

No formal hypothesis testing will be performed. Continuous data, unless otherwise specified, will be described using descriptive statistics (n, mean, standard deviation [SD], median, minimum, and maximum). Categorical data will be described using the subject count and percentage in each category. Non-zero percentages will be rounded to one decimal place, except 100%, which will be displayed without any decimal places. For the summary statistics of all numerical variables unless otherwise specified, minimum and maximum will be displayed to the same level of precision as reported, up to a maximum of three decimal places. Mean and median will be displayed to one level of precision greater than the data collected, up to a maximum of three decimal places. SD will be displayed to two levels of precision greater than the data collected, up to a maximum of three decimal places.

When count data are presented, the percentage will be suppressed when the count is zero, to draw attention to the non-zero counts. A row denoted 'Missing' will be included in count tabulations where specified in the table shells, to account for dropouts and missing values. The denominator for all percentages will be the number of subjects in the analysis set of interest, unless otherwise specified.

All data will be displayed in listings sorted by cohort, treatment, and subject ID – if applicable, screen failure subjects will be displayed in separately.

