### 4.2.2 Safety set

The safety set consists of all randomized subjects who have received at least one dose of study drug. Subjects will be analyzed according to the drug they actually received.

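### Testicular findings are given as a percentage of all dosed subjects, women included, so any non-zero incidence is understated for the men at risk

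*SAP*

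**What the plan says.** Read together, five provisions set the denominator for this row.

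- SAP 9.1.3 selects the events: "Testicular findings: AEs identified using SMQ as" *Fertility disorders*. For all four categories of special interest it says: "They will be summarized in a similar manner to that described in Section 9.1.1 for the following AESIs".
- SAP 9.1.1 tabulates the number and percentage of subjects with events, by system organ class and preferred term.
- SAP 9 fixes the population: "All safety analyses will be conducted using the Safety set, unless otherwise specified". SAP 4.2.2 defines it: "The safety set consists of all randomized subjects who have received at least one dose of study drug".
- SAP 4 gives the general rule: "The denominator for all percentages will be the number of subjects in the analysis set of interest, unless otherwise specified".
- Protocol 5.1 admits both sexes: "Male and female Chinese subjects aged 18 to 65 years, inclusive, at Screening". Protocol 6.3 states allocation ratios only; no quota or stratification by sex appears.

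Neither SAP 9.1.3 nor any other section restricts the testicular row to men.

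**The concern.** Women cannot have a testicular event. If they are counted in the denominator, the printed percentage is not the incidence among those at risk, and it depends on how many women happened to be allocated to the arm. Two arms with the same printed figure can have quite different incidences in men.

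The row matters because Table 2 of the protocol lists testicular toxicity as a potential risk of clinical significance. It cites findings in one animal species at about 1 to 2 times the expected clinical exposure, and says full reversibility could not be concluded. SAP 11 removes embryofetal toxicity from the list of special-interest events and adds nausea and vomiting. Testicular findings are then the only category confined to one sex, and the only one that the general denominator does not suit.

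**Working it through.** **Arm sizes.** These follow from Protocol 6.3 ("In PART-1, 32 subjects (16 in Cohort 1, then 16 in Cohort 2) will be randomized in a 3:3:2 ratio", and 4:1 in Part-2 with 10 subjects per cohort).

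- Part-1, per cohort: 16 × 3/8 = 6 low dose, 16 × 3/8 = 6 high dose, 16 × 2/8 = 4 placebo.
- Part-2, per cohort: 10 × 4/5 = 8 fosmanogepix, 10 × 1/5 = 2 placebo.
- Total: 2 × 16 + 2 × 10 = 52, which matches the planned enrolment of about 52.

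SAP 4 reports each active arm in its own column, so N is 6 in Part-1 and 8 in Part-2.

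**One case.** Let m be the number of men in the arm. The documents do not give m, so it is varied as an assumption.

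- Percentage as planned: 1/N
- Percentage among men: 1/m
- Factor of understatement: (1/m) ÷ (1/N) = N/m

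| Arm | Men (m) | As planned | Among men | Factor N/m |
|---|---|---|---|---|
| Part-1, N = 6 | 6 | 16.7% | 16.7% | 1.0 |
| | 5 | 16.7% | 20.0% | 1.2 |
| | 4 | 16.7% | 25.0% | 1.5 |
| | 3 | 16.7% | 33.3% | 2.0 |
| | 2 | 16.7% | 50.0% | 3.0 |
| Part-2, N = 8 | 8 | 12.5% | 12.5% | 1.0 |
| | 6 | 12.5% | 16.7% | 1.3 |
| | 4 | 12.5% | 25.0% | 2.0 |
| | 2 | 12.5% | 50.0% | 4.0 |

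The factor does not depend on the number of cases, provided all cases are in men.

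**Comparison between arms.** Take two Part-1 active arms with one case each, one arm with 5 men and the other with 2. Both print 16.7%. Among men the figures are 20.0% and 50.0%.

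**No cases.** The count is 0 on any denominator, and SAP 4 suppresses the percentage when the count is zero. What changes is how much a zero tells the reader. As an illustration, assume a true risk of 20% in men. The chance of seeing at least one case is 1 − 0.8^m:

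- m = 6: 0.74
- m = 5: 0.67
- m = 4: 0.59
- m = 3: 0.49
- m = 2: 0.36

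A reader who takes the column N of 6 as the number at risk credits the zero with the first figure, although one of the others may apply. The 20% is an assumption, and no planned output shows these probabilities.

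**The case against.** The strongest reply is that little turns on this.

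- **The men can be counted.** SAP 6.1 tabulates sex for the Safety set, and SAP 9.1 lists the events of special interest. In arms of 6 or 8 a careful reader can rebuild cases over men. This stands and limits the harm, but the printed percentage is still not the incidence in men.
- **The rule leaves room.** SAP 4 allows for exceptions and mentions table shells, which are not among the documents. SAP 9.1.1 tabulates only if appropriate, and SAP 9.1.3 asks only for a similar manner. A male denominator may exist in the shells. The SAP text does not state one, so its default applies.
- **The row will probably be empty.** The examinations in Protocol 8.2.1 name no genital examination. Table 9 of the protocol has no semen or testosterone test, and FSH serves only to confirm postmenopausal status. This makes a non-zero percentage unlikely; it does not make the percentage right if one occurs.
- **The study is descriptive.** No formal comparison between arms is planned, so no test result is affected. That is correct.

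Two stronger readings are tempting and do not hold. A reader might infer that the numerator is wrong as well, because *Fertility disorders* is not a male-specific name. The terms in that query are not in the documents, and SAP 11 refers to project reference documents that are not supplied; whether it would select an event in a woman cannot be settled here. A reader might also infer that zero-event results will carry too low an upper bound. No confidence interval for adverse event incidence is planned, so there is no bound to be wrong.

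**Conclusion.** The point holds as a minor, easily corrected defect of the written rules. SAP 4 and 9.1.3 together put women into the denominator for testicular findings, and any non-zero incidence is then understated by N divided by the number of men.

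The size rests on a sex mix that the documents do not give. The factor is 1 in an all-male arm and 2 when half the arm is male; with only 2 men it reaches 3 in a Part-1 arm and 4 in a Part-2 arm. The twofold figure is one point on that range and should not be quoted as the expected error. The conclusion also assumes that no table shell overrides the SAP text.

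For a zero count, what remains is a matter of presentation: the row does not show how many men were at risk.

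**What to change.** Add one sentence to SAP 9.1.3: testicular findings are counted and expressed as n/N among male subjects of the Safety set, with the number of men shown in each treatment column. If the table shells already do this, the SAP should say so.

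The restriction also keeps out of this row any event in a woman that the *Fertility disorders* query might select, so the contents of the query need not be resolved for this purpose.

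The cost is one SAP sentence and a sex filter in one table. Sex is already collected and summarised under SAP 6.1, so no new data are needed. The row concerns a secondary safety endpoint, and Protocol 9 requires a protocol amendment only for major changes to the primary endpoints or their analysis.

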#### 9.1.4 Medication errors

Medication errors are reported on a separate form in the eCRF. All medication errors will be listed.

## 9.2 Clinical laboratory evaluations

Local laboratory tests include chemistry, hematology, urinalysis, serology, and drug and alcohol screen parameters in accordance with the protocol Table 9.

Summary tables for laboratory parameters will be generated, including actual values and change from baseline values for clinical laboratory tests with numeric values at baseline and post-baseline scheduled assessments. Additionally, minimum and maximum post-baseline values will be summarized.

Laboratory data will also be summarized using shift tables where appropriate. Each continuous laboratory parameter values will be flagged as “low”, “normal”, or “high” relative to the normal ranges. Each categorical laboratory parameter values will be flagged as “abnormal” or “normal”. These categorical data will be summarized in shift tables comparing value at baseline visit with those at the relevant post-baseline visits, and the minimum and maximum post-baseline values, where appropriate.

Laboratory results will be graded using the CTCAE v5.0. These categorical data will be summarized in shift tables.

Laboratory data collected at unscheduled visits will be included in listings and will contribute to tables of shifts from baseline to minimum and maximum post-baseline.

If any laboratory value falls above or below the upper or lower level of quantification, the following rule will be applied for summary statistics: values reported as <xx or ≤xx will be analyzed as xx/2; values reported as >xx or ≥xx will be analyzed as xx.

Differentials will be displayed in the laboratory output as absolute values.

All clinical laboratory parameters will be presented in listings including normal ranges and indicating if the value is out of range.

### 9.2.1 Potential drug-induced liver injury (Hy's law)

Abnormal elevations in either aspartate aminotransferase (AST) or alanine aminotransferase (ALT) in addition to total bilirubin (TBili), that meet the criteria outlined in the protocol Appendix 5, are considered potential drug-induced liver injury (DILI). Subjects identified with abnormal elevation in one or more of these parameters will be identified and listed.

For the subjects identified, ALT, AST, TBili, as well as albumin, direct and indirect bilirubin, gamma-glutamyl transferase, prothrombin time, international normalized ratio, total bile acids, and alkaline phosphatase will be listed by visit.

### 9.3 Vital signs

Summary tables of observed values and changes from baseline as well as minimum and maximum post-baseline values will be presented for vital sign data, including weight (kg), systolic blood pressure (mmHg), diastolic blood pressure (mmHg), temperature (°C), pulse rate (beats/min), respiratory rate (breaths/minute), and oxygen saturation (%) at baseline and post-baseline scheduled assessments.

### 9.4 Electrocardiogram

Summary tables of observed values, changes from baseline as well as minimum and maximum post-baseline value will be presented for electrocardiogram data, including Heart Rate (bpm), PR Interval (msec), QRS Interval (msec), QT Interval (msec) and QTcF Interval (msec) at each scheduled visit.

The number and percentage of subjects with maximum post-baseline value and maximum change from baseline in the categories shown in Table 3 will be tabulated for QTcF Interval.

**Table 3 Safety QTcF assessment**

	Degree of prolongation (msec)		
Absolute value	> 450 – 480	> 480 – 500	> 500
Increase from baseline		> 30 – 60	> 60

A shift table from baseline to post-baseline ECG interpretations by visit will be displayed.

## 10 INTERIM ANALYSES

No interim analyses will be performed.

## 11 CHANGES IN THE PLANNED ANALYSIS

To harmonize the AESIs across fosmanogepix studies, the list of AESIs and the criteria for their identification have been updated. *Nausea* and *Vomiting* have been added, while

---

*Embryofetal toxicity* has been removed. The terms used to identify these AESIs are provided in Section 9.1.3 and are consistent with project reference documents.

## 12 APPENDICES

### Appendix 1 Adverse event date imputations

#### Imputation rules for partial dates

##### *Adverse event start date imputation*

Parameter	Missing	Additional conditions	Imputation
Start date for AEs	D	M and Y same as M and Y of first dose of study drug	Date of first dose of study drug
		M and/or Y not same as date of first dose of study drug	First day of month
	D and M	Y same as Y of first dose of study drug	Date of first dose of study drug
		Y is after Y of first dose	1 January
	D, M, Y	None – date completely missing	Date of first dose of study drug

D = day; M = month; Y = year; AE = adverse event.

Note: In all cases, if an estimated start date is after a complete stop date, use the first day of the stop date month.
